#### 11.3.1. Screening Design

In the screening phase, a Bayesian continuous futility monitoring rule will be implemented based on the rate of clinical benefit response in each of the 3 arms, respectively. An arm will be stopped if Prob (clinical benefit response > 25% | data) < 0.05. The above stopping rule suggests that, given the data obtained from patients who have already been evaluated in an arm, if there is less than a 5% chance that the rate of clinical benefit is greater than 25% we will terminate the arm. This decision rule generates the following stopping boundaries, assuming a beta(1,1) prior distribution for the clinical benefit response rate in each arm. Stop an arm i if [# of pts with clinical benefit response in arm i /# of pts evaluated in arm i]  $\leq 0/10$ , 1/17, where i = 1, 2, or 3. The operating characteristics of this rule are shown in Table 9.

Table 9	Operating Characteristics of Futility Monitoring - Maximum 20 AML Patients in	
Part 3 and Maximum 20 MDS Patients in Part 4		

			Sample Size	
Rate of clinical benefit response	Probability of stopping	P 25	P 50	P 75
0.05	0.822	10	10	17
0.10	0.54	10	17	20
0.15	0.313	17	20	20
0.20	0.165	20	20	20
0.25	0.082	20	20	20
0.30	0.039	20	20	20

After treating up to 10 evaluable AML patients (Part 3) and 10 evaluable MDS patients (Part 4) defined as patients who have completed at least 1 cycle of treatment

- If no CR, CRp, PR, major HI or SD is observed in Part 3, declare the treatment insufficiently active and no more AML patient will be treated with this dose regimen; if no CR, CRp, PR, major HI or SD is observed in Part 4, declare the treatment insufficiently active and no more MDS patients will be treated with dose regimen;
- If at least one CR, CRp, PR, major HI or SD is observed in Part 3, add AML patients to reach a total of 17 patients and if at least one CR, CRp, PR, major HI or SD is observed in Part 4, add MDS patients to reach a total of 17 patients.
  - o If less than two CR, CRp, PR, major HI or SD are observed in Part 3, declare the treatment insufficiently active for AML preceded by MDS previously treated with hypomethylating agents; if less than two CR, CRp, PR, major HI or SD are observed in Part 4, declare the treatment insufficiently active for MDS which were previously treated with hypomethylating agents.
  - o If at least two CR, CRp, PR, major HI or SD are observed in Part 3, add AML patients to reach a maximum of 20 patients; if least two CR, CRp, PR, major HI or SD are observed in Part 4, add MDS patients to reach a maximum of 20 patients

There is an early stopping rule for excessive toxicity. A dosing schedule will be declared to have excessive toxicity and no more patients will be treated with this dose regimen if among the first 10 patients treated with this dose regiment, there are > 2 patients experienced serious adverse events (excluding simple complications associated with myelosuppression such as neutropenic fever without shock or its complications from gram-negative bacteremia, anemia or mucosal bleeding, *e.g.*, epistaxis, due to thrombocytopenia easily controlled by transfusion) that are considered by investigator to be definitely, probably or possibly related to the study drug during the first two treatment cycles.

If a dosing schedule has at least 4 CR, CRp, PR, major HI, or SD, and the 30-day death rate is 20% or less, additional AML or MDS patients may be added to confirm the safety and tolerability of that dosing schedule.

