#### 3.5. Criteria for Study Discontinuation

This trial will be monitored by Cyclacel or its designees. The trial may be discontinued for safety concerns, slow accrual, or at the sponsor's discretion.

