#### 11.1.1. Screening Design

In the screening phase, a Bayesian continuous futility monitoring rule will be implemented based on the rate of CR plus CRi in each of the 3 arms of the AML stratum, respectively. An arm will be stopped if Prob (CR+CRi > 25% | data) < 0.05. The above stopping rule suggests that, given the data obtained from patients who have already been evaluated in an arm, if there is less than a 5% chance that the rate of CR+CRi is greater than 25% we will terminate the arm. This decision rule generates the following stopping boundaries, assuming a beta(1,1) prior distribution for the response (CR+CRi) rate in each arm. Stop an arm i if [ # of pts with CR or CRi in arm i / # of pts evaluated in arm i ]  $\leq$  0/10, 1/17, where i = 1, 2, or 3. The operating characteristics of this rule are shown in Table 8.

Table 8 Operating Characteristics of Futility Monitoring - Maximum 20 AML Patients

		Sample Size		
Rate of CR or CRi	Probability of stopping	P 25	P 50	P 75
0.05	0.822	10	10	17
0.10	0.54	10	17	20
0.15	0.313	17	20	20
0.20	0.165	20	20	20
0.25	0.082	20	20	20
0.30	0.039	20	20	20

After treating up to 10 evaluable AML patients defined as patients who have completed at least 1 cycle of treatment at each dosing schedule

- If no CR or CRi is observed, declare the treatment insufficiently active and no more AML patient will be treated with this dose regimen
- If at least one CR or CRi is observed, add AML patients to reach a total of 17 patients and
  - o If less than two CR plus CRi are observed, declare the treatment insufficiently active
  - o If at least two CR and CRi are observed, add AML patients to reach a maximum of 20 patients

For both AML and MDS patients, there is an early stopping rule for excessive toxicity. A dosing schedule will be declared to have excessive toxicity and no more patients will be treated with this dose regimen if among the first 10 patients treated with this dose regiment in either the AML or MDS stratum, there are > 2 patients experienced serious adverse events (excluding simple complications associated with myelosuppression such as neutropenic fever without shock or its complications from gram-negative bacteremia, anemia or mucosal bleeding, *e.g.*, epistaxis, due to thrombocytopenia easily controlled by transfusion) that are considered by investigator to be definitely, probably or possibly related to the study drug during the first two treatment cycles.

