If a dosing schedule within the AML stratum has at least 4 CR and CRi, and the 30-day death rate is 20% or less, additional AML patients may be added to confirm the safety and tolerability of that dosing schedule. If a dosing schedule within the MDS stratum has at least 4 CR, CRp, PR, and major HI, and the 30-day death rate is 20% or less, additional MDS patients may be added to confirm the safety and tolerability of that dosing schedule.

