#### 11.4. Data Analysis

The intent-to-treat population for Part 1 of the study will include all patients who have received at least one dose of study drug on an assigned dosing schedule. The primary analysis population will consist of patients who underwent randomization. The primary and secondary efficacy endpoints will be analyzed separately within the AML or MDS stratum. Additional patients accrued to a dosing schedule that has produced at least 20% CR/CRi will be analyzed separately. The rate of 1-year survival and that of CR, CRp, PR CRi, or hematological improvement, will be reported with 95% confidence interval. The intent-totreat population for Part 2 of the study will include all patients who have received at least one dose of the study drug. The rate of clinical benefit response (CR, CRp, PR, major HI or SD) and the rate of CR/CRp with be reported with 97.5% confidence interval. The intent-to-treat population for Part 3 and 4 of the study will include all patients who have received at least one dose of study drug on an assigned dosing schedule. The primary analysis population will consist of patients who underwent randomization. Additional patients accrued to a dosing schedule that has produced at least 20% clinical benefit response rate will be analyzed separately. Duration of CR, CRp, PR, CRi, HI, SD and overall survival will be estimated using the method of Kaplan and Meier. Patients who are discontinued from the study for reasons other than progression of disease will be censored at the time of the last response evaluation. The median number of transfusion-free weeks will be calculated for the 8 weeks

immediately prior to the first dose of study drug and while on study. For patients who required at least one transfusion of RBC or platelet within the 8 weeks immediately prior to the first dose of study drug, there will be a calculation of those who have achieved at least a 50% increase in the number of transfusion-free weeks on study over these at baseline, i.e., during the 8 weeks immediately prior to the receiving the first dose of the study drug.

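### The cohort added to confirm a schedule's safety has an entry condition, but no stated toxicity limit, death limit or maximum size while it accrues

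*Combined protocol and SAP*

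**What the plan says.** Section 11.3.1 (Parts 3 and 4) closes a schedule to further patients "if among the first 10 patients treated with this dose regiment, there are > 2 patients experienced serious adverse events". To count, the event must be judged by the investigator at least possibly related and must fall in the first two cycles. Simple complications of myelosuppression are excluded. Section 11.1.1 has the same rule for Part 1, worded "if among the first 10 patients treated with this dose regiment in either the AML or MDS stratum".

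After the tenth patient, accrual follows response counts. Futility monitoring is "based on the rate of clinical benefit response in each of the 3 arms, respectively", and an arm that passes at 17 goes on to its full size ("add AML patients to reach a maximum of 20 patients").

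A schedule with at least four responses and a 30-day death rate of 20% or less may then be extended. For Parts 3 and 4, "additional AML or MDS patients may be added to confirm the safety and tolerability of that dosing schedule"; for Part 1, "additional AML patients may be added to confirm the safety and tolerability of that dosing schedule", with a parallel sentence for MDS. Section 11.4 adds only that "Additional patients accrued to a dosing schedule that has produced at least 20% clinical benefit response rate will be analyzed separately", with a similar statement for Part 1. It reports 14-day and 30-day mortality with confidence intervals and attaches no limit.

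At trial level, section 3.5 says "The trial may be discontinued for safety concerns, slow accrual", or at the sponsor's discretion. Part 2 has no such toxicity rule and is outside this point.

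**The concern.** The added cohort exists to check safety, yet the plan names no result in it that would make anyone stop and look. The toxicity count is tied to a schedule's first 10 patients. The 20% death condition appears only in the sentence that permits patients to be added. A schedule that is too toxic but passed its first 10 by chance can therefore fill a cohort of unstated size with nothing but discretion to interrupt it. At stake are elderly patients exposed to a schedule whose excess toxicity is already visible in the accruing data.

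**Working it through.** **Inputs from the protocol.**
- Toxicity rule: 3 or more of the first 10 (11.1.1, 11.3.1).
- Entry condition: 30-day death rate of 20% or less (same sections). The denominator is not stated; I take 4 or fewer of 20.
- Planned numbers (3.4): 100 AML and 60 MDS in Part 1, then 36, 60 and 60 in Parts 2, 3 and 4. The synopsis total is about 325. Section 3.3 refers to 60 patients in the original Part 1 AML cohort.
- Accrual: 8 per month (3.4).

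**Assumed.** True qualifying-SAE rates p of 10 to 40%, because the plan states no unacceptable rate.

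**1. The section's own figures.** The plan gives no operating characteristics for the toxicity rule. The nearest figures are in Table 9 (futility, stop at 0/10 or 1/17). The formula is (1−p)^10 + 10p(1−p)^9 × (1−p)^7. At 0.05 this is 0.5987 + 0.2201 = 0.819 (Table 9: 0.822). At 0.30 it is 0.0282 + 0.0100 = 0.038 (Table 9: 0.039). The table reproduces closely, and it concerns response only.

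**2. Passing the toxicity rule.** P(pass) is the sum over k = 0, 1, 2 of C(10,k) p^k (1−p)^(10−k).
- p = 0.30: 0.0282 + 0.1211 + 0.2335 = 0.383
- p = 0.40: 0.0060 + 0.0403 + 0.1209 = 0.167

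**3. The entry condition on deaths.** P(4 or fewer of 20) is 0.96, 0.63 and 0.24 at true 30-day death rates of 10, 20 and 30%.

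**4. How large an added cohort could be.** In Part 1 AML, 100 − 60 = 40, or about 13 per schedule over three schedules. For the whole study, 100 + 60 + 36 + 60 + 60 = 316, and 325 − 316 = 9. Parts 3 and 4 and Part 1 MDS are each planned at exactly 3 × 20. The documents do not say how many of the 40 remain to be enrolled.

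**5. Same count applied to the added cohort alone.** For a cohort of at least 10, P(pause) = 1 − P(pass). With N the cohort size and t the patient who brings the third event, the mean number held back, with no delay and every pause leading to closure, is the sum over t = 3 to min(10, N) of C(t−1,2) p³ (1−p)^(t−3) (N−t).

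| True rate | P(pause), N ≥ 10 | Held back, N = 13 | Held back, N = 9 |
|---|---|---|---|
| 30% | 0.62 | 3.7 | 1.3 |
| 40% | 0.83 | 5.5 | 2.3 |

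A cohort of only 9 is paused less often: 1 − (0.0404 + 0.1556 + 0.2668) = 0.54 at 30% and 1 − (0.0101 + 0.0605 + 0.1612) = 0.77 at 40%.

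Delay reduces the saving. With events spread evenly over 8 weeks, and accrual to the schedule between 1.3 per month (8 shared by six arms) and 8 per month, the saving for N = 13 runs from 3.3 down to 0.5 at 30% and from 4.9 down to 1.0 at 40%.

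**6. Unwanted pauses.** The SAE check pauses with probability 0.07 at a true rate of 10% and 0.32 at 20%. A death review after 10 patients that flags 3 or more has the same binomial: 0.07, 0.32 and 0.62 at 10, 20 and 30% deaths. With both rates at 20%, at least one check fires with probability 1 − 0.678² = 0.54 if they are independent, and no less than 0.32 if they overlap. With both at 10% and independent, it is 1 − 0.930² = 0.14.

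**The case against.** - **Other safeguards exist.** Section 3.5 allows discontinuation for safety concerns. Section 6.2 prescribes dose reductions and generally removes a patient who needs more than two. Section 8.2 requires SAE reporting. A reader might infer that a toxic schedule could not be stopped after patient 10; the documents do not support that. What stands is narrower: none of these gives a number for a schedule.
- **The death condition may continue.** The sentence could be read as a standing requirement. The text does not settle this, and it gives no time or denominator for rechecking.
- **The rates are assumed.** The nearest observed figure is a 10% 30-day death rate on 400 mg b.i.d. (3.3). Most starting doses in Parts 3 and 4 are no higher than schedules already used. This is fair, so the figures show what the rule can detect and do not predict toxicity.
- **The cohort may be small.** A reader might assume 20 added patients per schedule and a correspondingly larger saving. No section supports 20. Only Part 1 AML has clear room.
- **Patients 11 to 20 are also unmonitored.** A reader might infer that they need a second look. Pausing at a sixth event in 20 would flag 26% (54%) of arms that passed, but even with no delay it spares only 0.5 (1.2) patients per passing arm. That does not justify a further rule.
- **A pause is still discretion.** True. The gain is a review that must take place and be documented, and the held-back figures are upper values that apply only if each pause ends accrual.

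**Conclusion.** The point holds for the added cohort in Parts 1, 3 and 4: an entry condition is stated, and no toxicity limit, death limit or maximum size applies while it accrues. At assumed true rates of 30% (40%), the chance that a schedule reaches that stage without triggering its only toxicity rule is 0.38 (0.17).

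The number of patients protected is modest: at most about 4 (6) in a cohort of 13 and 1 (2) in a cohort of 9, and fewer with delay. These figures rest on the assumed rates, on inferred cohort sizes and on every pause leading to closure. This is a worthwhile, cheap improvement. It is not evidence that the schedules are unsafe or that safety oversight is absent.

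**What to change.** For any added cohort still to be enrolled:

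1. Count it on its own, with the event definition already in the plan. Pause accrual for a documented medical-monitor decision (resume, reduce dose or close) if more than 2 of its first 10 patients have qualifying related SAEs.
2. State that the 20% 30-day death condition continues to apply, and recheck it at a fixed review, for example after 10 patients.
3. State a maximum cohort size.
4. Require sites to notify the medical monitor promptly of qualifying events and 30-day deaths in the cohort. Section 8.2 lets hospitalizations for sepsis, pneumonia or neutropenic colitis associated with myelosuppression, and deaths from AML progression, go on the case report form without a report to the safety desk. Some of these would count.

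The cost is protocol wording, a small change in reporting flow and some unnecessary reviews: 0.07 at a true SAE rate of 10% and 0.32 at 20%, with more from the death review. At 20% rates a pause is common, so it must be a review and not an automatic closure. Toxicity after cycle 2 stays outside the count.

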#### 11.3.2. Selection Design

Assuming that at least 2 dosing schedules show activity and that their toxicity profile is similar, a selection design will be used to choose the dosing schedule with the better observed 1-year survival rate. If the better dosing schedule has a true 1-year rate of 45% and the worse dosing schedule a true 1-year rate of 30%, the trial has better than 80% probability to choose the correct dosing schedule if 20 patients have been treated with each dosing schedule.

No formal hypothesis testing will be carried out for the 1-year survival rate. Instead, we will estimate the 1-year survival rate for each dosing schedule, along with the 95% confidence interval. Given a total of 20 patients in an arm and assuming a 1-year survival rate of 45%, the half-width of the 95% confidence interval will be 0.22. On the other hand, if assuming a 1-year survival rate of 30%, the half-width of the 95% confidence interval will be 0.20.

#### 11.3.3. Stratification Factor

AML and MDS patients will be stratified by prior treatment with decitabine (Yes or No). The reason is that patients who have been treated with decitabine may respond differently to sapacitabine than those who have only received azacitidine. 

#### 11.4. Data Analysis

The intent-to-treat population for Part 1 of the study will include all patients who have received at least one dose of study drug on an assigned dosing schedule. The primary analysis population will consist of patients who underwent randomization. The primary and secondary efficacy endpoints will be analyzed separately within the AML or MDS stratum. Additional patients accrued to a dosing schedule that has produced at least 20% CR/CRi will be analyzed separately. The rate of 1-year survival and that of CR, CRp, PR CRi, or hematological improvement, will be reported with 95% confidence interval. The intent-totreat population for Part 2 of the study will include all patients who have received at least one dose of the study drug. The rate of clinical benefit response (CR, CRp, PR, major HI or SD) and the rate of CR/CRp with be reported with 97.5% confidence interval. The intent-to-treat population for Part 3 and 4 of the study will include all patients who have received at least one dose of study drug on an assigned dosing schedule. The primary analysis population will consist of patients who underwent randomization. Additional patients accrued to a dosing schedule that has produced at least 20% clinical benefit response rate will be analyzed separately. Duration of CR, CRp, PR, CRi, HI, SD and overall survival will be estimated using the method of Kaplan and Meier. Patients who are discontinued from the study for reasons other than progression of disease will be censored at the time of the last response evaluation. The median number of transfusion-free weeks will be calculated for the 8 weeks

immediately prior to the first dose of study drug and while on study. For patients who required at least one transfusion of RBC or platelet within the 8 weeks immediately prior to the first dose of study drug, there will be a calculation of those who have achieved at least a 50% increase in the number of transfusion-free weeks on study over these at baseline, i.e., during the 8 weeks immediately prior to the receiving the first dose of the study drug.

The early death rate is defined as death due to any cause occurring within 14 days after the first dose of the study drug and will be reported with 95% confidence interval. In addition, 30-day mortality rate defined as death due to any cause occurring within 30 days after the first dose of the study drug will also be reported with 95% confidence interval. Treatment-emergent AEs will be summarized by system organ class and preferred term coded in accordance with the version of MedDRA that is most recent at the start of the study. Summaries of early withdrawal, deaths, SAEs and the number of hospitalized days measured from the first dose of the study drug to the date when the patient is discontinued from the study will be presented. The clinical significance of laboratory changes will be discussed. The safety analysis will be performed separately within the AML and MDS stratum as well as combining the two strata.

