### 4.3. Removal of Patients from Therapy

Patients have the right to withdraw from the study at any time for any reason. The investigator has the right to withdraw patients from the study according to his/her discretion. When a patient discontinues treatment early, every effort will be made to conduct a post-treatment follow-up visit within 4 weeks after the last dose of study drug or prior to the initiation of new treatment. This post-treatment evaluation may be conducted over the phone if the patient is unable to return to the clinic. The reason(s) for withdrawal must be recorded.

Criteria for terminating participation in the study are listed below:

- Clinically significant progressive disease defined as > 50% increase in the percentage of blasts in bone marrow or peripheral blood over baseline to reach at least 20% blasts in bone marrow or peripheral blood by two assessments while on treatment with an adequate dose
- Lack of efficacy refers to treating physician's judgment that patients are unlikely to benefit from continuation of treatment despite not meeting the criterion of clinically significant progressive disease.
- Unacceptable toxicity
- Patient withdrawal of consent for treatment
- Investigator's discretion that it is in the best interest of the patient to withdraw
- Intercurrent illness: a condition, injury, or disease unrelated to cancer in the opinion of the investigator, that renders continuing sapacitabine treatment unsafe or regular follow-up impossible

- General or specific changes in the patient's condition that renders the patient ineligible for further treatment
- Noncompliance with study medication or protocol-required evaluations and followup visits
- Termination of the clinical trial by the sponsor

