#### 9. EFFICACY ASSESSMENT

The primary efficacy endpoint of Part 1 of this study is 1-year survival, i.e., the proportion of patients who are alive at 1-year measured from the date of the randomization. Secondary efficacy endpoints are the rate of CR, CRp, PR or CRi or hematological improvement and their corresponding durations, transfusion requirements and number of hospitalized days. The primary efficacy endpoints of Part 2 of this study are the rate of clinical benefit response (CR, CRp, PR, or major HI) and the rate of complete response (CR or CRp). Secondary efficacy endpoints are response durations, transfusion requirements, number of hospitalized days, and overall survival. The primary efficacy endpoint of Part 3 and 4 of this study is 1-year survival rate. Secondary efficacy endpoints are the rate of clinical benefit response (CR, CRp, PR, major HI or SD) and their corresponding durations, transfusion requirements, number of hospitalized days and overall survival.

The tissue samples supporting the diagnosis of AML or MDS, and the responses to sapacitabine may be submitted for central review.

Table 6 Response Criteria

Passansa Description					
Response	Description				
Complete Remission (CR) 	Normalization of peripheral neutrophils to ≥1000 /µL, platelet to ≥100,000/µL within 2 weeks of bone marrow biopsy/aspirate, and bone marrow to ≤5 % blasts; independent of transfusions*; and no extramedullary leukemia.				
Complete remission with incomplete platelet count recovery (CRp) 	Normalization of bone marrow to $\leq$ 5% blasts; peripheral neutrophils $\geq$ 1000 /µl, platelet $<$ 100,000 /µL within 2 weeks of bone marrow biopsy/aspirate; independent of transfusions*; and no extramedullary leukemia.				
Complete remission with incomplete blood count recovery (CRi) 8	Normalization of bone marrow to $\leq$ 5% blasts; peripheral neutrophils $<1000~/\mu$ L, platelet $<100,000/\mu$ L within 2 weeks of bone marrow biopsy/aspirate; independent of transfusions *; and no extramedullary leukemia.				
Partial Remission (PR) 8	Normalization of peripheral neutrophils to $\geq 1000 \ / \mu L$ , platelet to $\geq 100,000/\mu L$ within 2 weeks of bone marrow biopsy/aspirate, $\geq 50\%$ decrease in bone marrow blasts over pretreatment but still >5%; independent of transfusions * .				
Hematological improvement (HI) 9	Major response:				

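### Section 11.4 has one censoring rule, built for response durations but not limited to them, and gives overall survival no censoring rule of its own

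*Combined protocol and SAP*

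**What the plan says.** Section 11.4 (Data Analysis) states: "Duration of CR, CRp, PR, CRi, HI, SD and overall survival will be estimated using the method of Kaplan and Meier". The sentence after it says that patients discontinued "for reasons other than progression of disease will be censored at the time of the last response evaluation". That is the only censoring rule in the documents. None uses the date last known alive, and overall survival has no stated start date or event definition.

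Section 4.3 lists the reasons for ending participation. Besides progression they include "Unacceptable toxicity"; lack of efficacy ("Lack of efficacy refers to treating physician's judgment that patients are unlikely to benefit from continuation of treatment"); and intercurrent illness "that renders continuing sapacitabine treatment unsafe or regular follow-up impossible". Death is not on the list.

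Section 9 makes overall survival a secondary efficacy endpoint in Part 2 ("Secondary efficacy endpoints are response durations, transfusion requirements, number of hospitalized days, and overall survival") and in Parts 3 and 4 ("their corresponding durations, transfusion requirements, number of hospitalized days and overall survival"). Section 8 also lists it as a safety parameter. The primary endpoint is described separately: for Part 1, Section 9 defines it as the proportion alive one year after randomization.

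**The concern.** In an overall survival analysis the event is death from any cause, and progression has no role. The Section 11.4 rule, applied to survival, sets a patient's follow-up time by the reason for leaving and the date of the last response assessment. Later follow-up is discarded, including a known date of death. A patient who leaves for progression and then dies remains an event, while one who leaves for toxicity and then dies does not. Nothing about survival justifies that difference.

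Kaplan-Meier estimation is unbiased only if censored patients have the same later risk as those still followed. Several exit reasons in Section 4.3 plausibly mark patients at higher risk of death. Where they do, the rule raises the curve, and it raises it more in an arm that loses more patients this way. The curve could then disagree with the primary proportion alive at 1 year in the same arm.

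**Working it through.** **1. The plan's own precision.** Sections 11.1.2 and 11.3.2 state 95% half-widths for 1-year survival with 20 patients per arm. Using 1.96 × √(p(1−p)/20):

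- p = 0.45: 1.96 × √(0.45 × 0.55/20) = 0.218 (stated 0.22)
- p = 0.30: 1.96 × √(0.30 × 0.70/20) = 0.201 (stated 0.20)

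Both reproduce, and they give a scale for judging any bias.

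**2. The mechanics in one arm.** Take 20 patients with 11 deaths evenly spaced before 12 months and 9 alive afterwards. With all deaths counted, the estimate is 9/20 = 45%. Now censor some of the patients who die, each 1.5 months before death. Averaged over which patients are chosen, the 12-month estimate is:

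| Deaths dropped | Estimate |
|---|---|
| 0 | 45% |
| 1 | 48% |
| 2 | 52% |
| 3 | 55% |

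This shows direction only, because every censored patient here is one who was about to die. In a control run with exits unrelated to prognosis, the curve stayed at about 45% and 30% when those were the true values.

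**3. A fuller model.** Only the 30% comes from the documents (the planning rate for the worse schedule). The other inputs are assumptions:

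- exponential times, with monthly response evaluations
- live-exit hazard μ = ln 2/3 = 0.231 per month (median time to live exit 3 months)
- 30-70% of live exits for progression
- post-exit death hazard h times the on-study hazard λ, with h from 1 to 3

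The on-study hazard λ is chosen so that true 12-month survival is 30%:

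S(12) = e^(−12(λ+μ)) + μ[e^(−12hλ) − e^(−12(λ+μ))]/(λ+μ−hλ) = 0.30

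For h = 1 this reduces to λ = −ln(0.30)/12 = 0.100 per month. Non-progression live exits are then censored at the last evaluation, and Kaplan-Meier is read at 12 months (200,000 simulated patients per scenario).

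*On-study deaths counted as events:*

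| Post-exit hazard ratio h | 12-month estimate (true 30%) |
|---|---|
| 1 | 28.6-29.6% |
| 2 | 31-34% |
| 3 | 32-37% |

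The error is about −1 to +7 points. At h = 1 there is no upward bias. The slight shortfall arises because censoring is moved back from the exit to the preceding evaluation, which removes time alive.

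*On-study deaths also treated as non-progression exits:* 41-57%, an error of +11 to +27 points.

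**4. Sensitivity to one definition.** If the 3 months is instead the median time to any exit, death included, the ranges become about 29-38% (deaths counted) and 44-71% (deaths censored). The first range barely moves, but the worst case does.

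**5. Which decisions use the curve.** Selection uses the observed 1-year survival rate without formal testing (11.1.2, 11.3.2). Futility uses response or clinical benefit, and toxicity stopping uses serious adverse events (11.1.1, 11.3.1). Part 2 uses response rates (11.2). None refers to the Kaplan-Meier survival curve.

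**The case against.** The strongest reply is that the rule was never meant for survival. Its terms, progression and last response evaluation, belong to duration endpoints: Section 9 ends response durations at documented recurrence or progression. Exempting progressors from censoring makes sense for a duration and none for survival. This is probably what the authors intended, so a reader should not infer that the survival curve will certainly be too high. What stands is that the text does not say so and supplies no alternative. An analyst who follows it literally censors survival wrongly; one who departs from it must choose a survival rule after open-label data are in hand.

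A reader might also take 41-57% as the expected size. The documents do not support that. It requires a death on study to be a discontinuation for a reason other than progression, and Section 4.3 does not list death as a reason for leaving.

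Finally, a reader might infer that a more toxic schedule could be selected because of this rule. Selection does not use the curve. Section 11.4 separately reports all-cause mortality at 14 and 30 days, deaths, serious adverse events and early withdrawals, so early toxic deaths stay visible. Section 9 lists survival as secondary in Parts 3 and 4, but the Section 2 objectives for those parts do not. These points limit the consequence; they do not supply the missing rule.

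**Conclusion.** The point holds as a defect of specification: one unrestricted censoring rule, and none suited to overall survival. Applied literally, it discards known deaths and biases the curve upward if non-progression exits predict death. Under the assumed inputs the error is about −1 to +7 points around a true 30% when on-study deaths count, against a stated half-width of 20 points at n = 20. The larger figures belong to a second literal reading and are a worst case.

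The direction depends on exits being related to prognosis. The Section 4.3 reasons make that plausible, but the documents give no data on it. The primary result is affected only if the 1-year rate is taken from this curve; Section 11.4 does not name its estimator. The correction is still worth making before analysis, because survival is a named efficacy endpoint in Parts 2 to 4 and a safety parameter.

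**What to change.** In Section 11.4, limit the censoring sentence to the durations of CR, CRp, PR, CRi, HI and SD. Then add: *Overall survival runs from randomization (Part 2: registration) to death from any cause. Patients not known to have died are censored at the date last known alive, whatever the reason for leaving treatment or study.*

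The text change is one or two sentences, with no added patients. It is not quite free: Section 6.4 schedules only one contact, within 4 weeks of the last dose, and a last-known-alive rule works only if later deaths are ascertained. The 1-year endpoint in Parts 1, 3 and 4 already needs survival status beyond that contact, so the team should confirm that it is collected and also used for overall survival. For Part 2, where survival is secondary, the source of later survival status should be stated.
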